In order to determine an appropriate sample size, an a priori power analysis was performed. We chose to use isometric quadriceps strength at two weeks as the primary outcome variable. Using an alpha level of 0.05 and the standard deviation and minimal clinically important difference reported by Husted et al. (Trials, 2018) of 0.22 Nm/kg and 0.15 Nm/kg, respectively, a sample size of 70 total patients (35 patients per group) would be 80% powered to detect clinically important differences (G*Power, version 3.1).

Data collection will coincide with four regularly-scheduled patient visits: preoperative and 2, 6, and 12 weeks after surgery. Participants will complete isometric quadriceps testing at each study visit, and will be asked to complete the KOOS,JR, VR-12, and VAS pain scale questionnaires. We will also record the participant's opioid consumption per our standard of care, as well as whether the patient is able to walk without an assistive device and/or self-reports the ability to navigate stairs. Beginning at the 6-week postoperative visit, patients will be asked to complete the five times sit-to-stand test. The primary outcome variable, isometric quadriceps strength at 2 weeks, will be compared between groups using a two-tailed independent t-test. All continuous secondary variables will be assessed using group x time repeated measures ANOVAs. The prevalence of patients that can walk without an assistive device and/or navigate stairs at 2, 6, and 12 weeks will be compared between groups using chi-square or Fisher Exact tests as appropriate.

Attachments

Subject Recruitment Methods & Advertising

Describe how the study team will identify and recruit subjects. Please consider the following items and provide additional information as needed so that the IRB can follow each step of the recruitment process.

- How will the study team identify potential participants?
- Who will first contact the potential subjects, and how?
- Will you use advertisements? If so, how will you distribute those?
- How and where will the research team meet with potential participants?
- If applicable, describe proposed outreach programs for recruiting women, minorities, or disparate populations.
- How you will minimize undue influence in recruitment?
- Attach copies of all recruiting and advertising materials (emails, verbal scripts, flyers, posts, messages, etc.).

For additional information on recruiting and advertising:

- [IRB Application Instructions - Advertisements](#)

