Five Times Sit-to-Stand Test: The five-repetition sit-to-stand is commonly used to measure mobility and function in older adults. Participants are positioned in a standard 16" office chair with their arms at their sides and back located against the back of the chair. Participants are instructed to "Please stand up straight as quickly as you can 5 times, without stopping in between. Keep your arms folded across your chest. I'll be timing you with a stopwatch. Ready, begin." The test is timed using a stopwatch and the timer is stopped when the individual achieves a standing position on the 5th trial. To ensure safety, we will utilize a four-legged chair that does not have wheels, and the chair will be placed so it backs against a wall to prevent the chair from moving during the test. While the participant will be asked to complete the test without using the chair's armrests, the armrests are available for balance should they need assistance. If at any visit the participant cannot complete one practice repetition of sit to stand without using the armrests, we will not ask them to participate in the test at that visit.

Patient-Reported Outcomes: Participants will be asked to complete four questionnaires at each study visit. Participants will be asked to complete the Knee injury and Osteoarthritis Outcome Score, Joint Replacement (KOOS JR) questionnaire which is a 7-item instrument validated to assess patient outcomes following knee arthroplasty. Other questionnaires will include the Veterans Rand-12 (VR-12) which is a 12-item instrument that assesses physical and mental health and a Visual Analogue Scale (VAS) to assess pain and patient confidence in their knee. In addition, a study-specific questionnaire will be used to assess whether the patient is able to ambulate without an assistive device and to determine the method by which the patient navigates stairs (one-step at a time, requires the use of a handrail, etc.).

Attachments

Attach Type	File Name
ResearchProcedures	Aquamantys Page 4 Study Flow Chart.pdf

Data Collection & Research Materials

In this section, please provide the following:

- Describe all sources or methods for obtaining research materials about or from living individuals (such as specimens, records, surveys, interviews, participant observation, etc.), and explain why this information is needed to conduct the study.

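### The method of climbing stairs is collected but has no planned analysis: the plan tests only an undefined able/unable proportion, joined to walking by an and/or

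*Combined protocol and SAP*

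**What the plan says.** In the combined protocol and SAP, Research Procedures (Patient-Reported Outcomes), a study-specific questionnaire given at each study visit records walking without an aid and is also used "to determine the method by which the patient navigates stairs (one-step at a time, requires the use of a handrail, etc". This is information about how stairs are managed, not only whether they are.

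Study Design describes the same item differently. There the study records "whether the patient is able to walk without an assistive device and/or self-reports the ability to navigate stairs". The analysis sentence then names "The prevalence of patients that can walk without an assistive device and/or navigate stairs at 2, 6, and 12 weeks", which "will be compared between groups using chi-square or Fisher Exact tests as appropriate".

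The only other method given for secondary outcomes is repeated measures ANOVA, and that is for continuous variables. No sentence assigns an analysis to the method of stair climbing, and none maps the methods to able or unable. The questionnaire is listed as an attachment, but its response options are not in the text.

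The sample size rests on a different outcome: "We chose to use isometric quadriceps strength at two weeks as the primary outcome variable". No power is claimed for stairs.

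**The concern.** Three things are left open.

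- **The grades go unused.** Two patients who manage stairs by different methods may fall into the same cell of the planned two-by-two table. The background text before Objectives names stair climbing among the milestones that preserved quadriceps function might bring forward, so an effect on how stairs are climbed is within the trial's own rationale.
- **The cut-point is unstated.** Able could mean by any method, or only without a rail, or only step over step. Left undefined, it could be chosen after the data are seen.
- **The and/or is ambiguous.** It can mean two separate outcomes, a composite met by either, or a composite that needs both. An either-one composite has a proportion at least as high as that for stairs alone; a both-required composite has one no higher. The three readings can give different results from the same data.

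At stake is the chance of detecting a real difference in stair function, and a clear prior definition of what is being tested.

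**Working it through.** **1. The plan's own figure.** Inputs from Study Design: SD 0.22 Nm/kg, difference 0.15 Nm/kg, two-sided alpha 0.05, power 80%. The standardised difference is d = 0.15/0.22 = 0.682. The normal approximation n = 2(1.96 + 0.84)²/d² gives 34 per arm. The noncentral t calculation gives 34.75, so 35 per arm, with 80.3% power. The stated 35 per arm is reproduced. It concerns quadriceps strength only.

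**2. Inputs for stairs.** From the plan: 35 per arm, chi-square or Fisher exact test. I take alpha as two-sided 0.05. Everything else is an assumption, because the documents give no stair-ability rate and do not show the response options: four ordered grades (unable first, best last) and a common odds ratio (OR) between arms.

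**3. Treated-arm rates.** Under proportional odds, each cumulative odds in the treated arm is the control odds divided by the OR. For example, at 90% able in control the odds of being unable are 0.10/0.90 = 0.111. Dividing by 3 gives 0.037, so 3.6% are unable and 96.4% able.

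**4. Tests.**

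- Able/unable: exact enumeration over all pairs of binomial counts, using uncorrected chi-square, or Fisher when an expected count is below 5.
- Graded: tie-corrected Wilcoxon, z = (W − E)/√V. W is the sum of mid-ranks in the treated arm, E = n(N + 1)/2 = 35 × 71/2 = 1242.5, and V = (n²/12)[(N + 1) − Σ(t³ − t)/(N(N − 1))], where t is the number of patients in each grade. This was simulated.

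**5. Results at OR 3.**

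| Control grades, unable to best (%) | Control able | Treated able | Rank test power | Able/unable power |
|---|---|---|---|---|
| 50/30/15/5 | 50% | 75.0% | 70% | 59% |
| 30/40/20/10 | 70% | 87.5% | 70% | 43% |
| 20/40/30/10 | 80% | 92.3% | 70% | 26% |
| 10/45/30/15 | 90% | 96.4% | 69% | 5% |
| 5/35/35/25 | 95% | 98.3% | 69% | 0.4% |

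A separate simulation of the able/unable test gave 60%, 42% and 27% for the first three rows, within about one percentage point.

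**6. Other effect sizes.** At OR 2 the rank test reaches only about 34–35%, against 28% (50% able), 22% (70%) and 3% (90%) for able/unable. At OR 4 it reaches 87–88%, against 77%, 57% and 6%.

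**7. A check that needs no ordinal model.** If 90% of controls are able, even 100% in the treated arm gives the able/unable test only 13% power. If 80% are able, 100% in the treated arm gives 73%.

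**The case against.** The strongest reply is that the proportion reaching a milestone is a legitimate and easily read outcome. It matches the background text, it is secondary, and the plan claims no power for it. Preferring an ordinal test is then largely a matter of efficiency. With half of controls able, the planned test keeps most of the power (59% against 70% at OR 3).

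The assumptions also favour the rank test. Proportional odds suits it, and four ordered grades are not documented. Going one step at a time and needing a handrail are not mutually exclusive, so the questionnaire may hold separate items with no single natural order.

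A reader might go further and infer that almost every patient will be able, so that the outcome sits at a ceiling and most of the information is lost. The exclusion of people who cannot safely go home on day 0 or 1, and discharge tied to functional goals, make a high rate plausible if able means by any method. But no section makes stair climbing a discharge requirement, and the background text treats it as a milestone still to be reached after surgery. Nor does any section say that a patient going one step at a time with a rail counts as able.

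The milestone argument stands as a reason to keep the percentage. The limits on the assumptions stand as limits on the size of the loss. Neither supplies an analysis for the graded response, a cut-point, or a reading of the and/or.

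**Conclusion.** The mismatch holds on the text alone: stair method is collected, only an undefined yes/no proportion is tested, and the proportion may or may not be merged with walking.

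The loss from the planned test is conditional. In every scenario tried the rank test had more power. The gap at OR 3 runs from about 11 percentage points (50% of controls able) to more than 60 (90% or more able). It rests on four ordered grades, proportional odds, 35 per arm analysed, and a control rate that the documents do not give.

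Three stronger statements are not supported. That the outcome is near its ceiling, or has very low power, would need roughly 85–90% or more of controls to be able. That most of the information is discarded is not true in general. That a real benefit would be reported as no difference should read could, and for this item only: strength, the other questionnaires, opioid use and sit-to-stand have their own analyses. The primary outcome and the total of 70 are unaffected.

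**What to change.** Amend the analysis text before unblinding:

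1. State walking without an aid and stair climbing as two separate secondary outcomes, and drop the and/or.
2. Fix the order of the stair responses from best to worst, with a combined ranking if step pattern and handrail use are separate items. Define which responses count as able.
3. Compare arms on the graded response at 2, 6 and 12 weeks by a Wilcoxon test, or by proportional-odds regression adjusted for the preoperative stair response. The questionnaire is planned for every visit, including the preoperative one, so that response should be available.
4. Keep the percentage able as a descriptive milestone at each visit.

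The cost is wording only: no new data, visits or patients. The downsides are that the ordering must be settled in advance, and that an ordinal effect is slightly harder to interpret than a percentage. The adjusted analysis was not simulated here; the power figures are for the unadjusted rank test.

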Each Section/Subsection in the menu on the left must have a checkmark beside it (except this Submission section) indicating the Section/Subsection has been completed. Otherwise your submission for IRB review and approval cannot be sent to the Office of Research Integrity/IRB.

If applicable, remember to update the Approval Letter Details text box under the Additional Information section

If your materials require review at a convened IRB meeting which you will be asked to attend, it will be scheduled on the next available agenda and you will receive a message to notify you of the date.

If you are making a change to an attachment, you need to delete the attachment, upload a highlighted version that contains the changes (use Document Type of "Highlighted Changes"), and a version that contains the changes without any highlights (use the appropriate Document Type for the item(s)). Do **not** delete approved attachments that are still in use.

Your protocol has been submitted.

[Download all](#)

	Document Type	File Loaded	Document Description	File Size	Modified By	Mod Date
↳	ApprovalLetter	ApprovalLetter.pdf		0.079	[name]	6/23/2023 8:24:58 AM
↳	AddInfoProduct	Memo Aquamantys.docx	Memo & Response to Comment	0.012	[name]	5/16/2023 3:45:26 PM
↳	AdditionInfoConsiderations	[name] HSP citiCompletionReport.pdf	[name]	0.150	[name]	7/29/2021 7:36:34 AM
↳	AdditionInfoConsiderations	[name].pdf	[name] HSP certificate	0.400	[name]	10/20/2020 2:20:56 PM
↳	StudyDevice	121918, Form P, Aquamantys - (Clean).pdf	121918 Form P, Aquamantys (Clean)	0.840	[name]	1/14/2019 9:56:16 AM
↳	AddInfoProduct	Aquamantys 510k letter.pdf	Aquamantys 510K Letter	0.304	[name]	11/15/2018 9:36:18 AM
↳	AdditionInfoConsiderations	AuthorizationAssuranceForm05292018.pdf	Department Authorization Letter	0.033	[name]	11/15/2018 9:28:10 AM
↳	ResearchProcedures	Aquamantys Page 4 Study Flow Chart.pdf	Aquamantys Page 4 Study Flow Chart	0.012	[name]	11/14/2018 12:05:08 PM
↳	DataCollection	VR12.pdf	THE VETERANS RAND 12-ITEM HEALTH SURVEY (VR-12)	0.249	[name]	11/14/2018 11:22:12 AM
↳	DataCollection	Visual Analogue Scale.docx	Visual Analogue Scale	0.013	[name]	11/14/2018 11:21:02 AM
↳	DataCollection	KOOS-JR-2015.pdf	KOOS, JR. KNEE SURVEY	0.145	[name]	11/14/2018 11:20:03 AM
↳	DataCollection	Knee Function Questionnaire.docx	Knee Function Questionnaire	0.015	[name]	11/14/2018 11:17:46 AM

Protocol Changes

No Changes

There are no recorded changes tracked for this protocol.

